Disease-specific concerns related to the infusions include: interference with point of care glucometer readings (resulting in falsely high results), which is not seen in venous laboratory glucometer readings. In large doses of vitamin C, hyperoxaluria can be observed in 1-10% of patients, raising concerns primarily for patients with active renal calculus or those prone to recurrent renal calculi. Studies involving patients with advanced cancer have reported infrequent side effects consisting of nausea, vomiting, dizziness, and headache.

Other potential risks of participating in the research study include the mild risks of blood draws (bleeding, infection, damage to soft tissue). To minimize this, research-related blood draws will be taken from existing intravenous catheters placed for standard of care purposes (if applicable) or combined with clinically-indicated lab draws to avoid repeat phlebotomy.

2 * Describe how the risks / harms will be minimized:

Diabetics will be excluded if they are on insulin therapy and/or if they have uncontrolled diabetes, defined as a glycosylated hemoglobin of greater than or equal to 8%. While admitted periprocedurally, signs will be posted inside and outside of the patient rooms as a warning that point of care glucose readings should not be considered reliable within 36 hours of the infusion, in case this is ordered clinically. In-services will be given to the nursing staff in all involved clinical areas to educate them on the effect of high dose ascorbic acid infusions on point of care glucometers.

Patients with active renal calculus or those deemed prone to recurrent renal calculi will be excluded from the study.

Below is our protocol for addressing the blood glucose monitoring concerns:

Guidance for blood glucose monitoring in patients enrolled in investigational Vitamin C Studies under this IND:

Glucose levels in this study population are checked daily as standard of care, and point of care testing is not usually needed. However, all studies under this IND follow the glucose monitoring plan outlined below. If additional glucose draws are required for a participant in this study, all additional draws outside of standard of care will be billed to the study. Additional glucose draws, if needed, will be determined on an as needed basis by the clinical team.

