Ascorbic acid is known to artefactually raise POC blood glucose readings; however, it does not raise blood glucose readings from a basic metabolic panel or glucose results using the gas lab. Thus, extreme care must be taken to assure an accurate blood glucose level from a metabolic laboratory (BMP) or arterial blood gas panel before initiating any insulin therapy, including sliding scale or scheduled insulin.

Guidance for blood glucose monitoring in patients enrolled this study:

◆ Critical care Nursing and Physician leadership at all study sites must be informed of vitamin C's effect on point of care (glucometer) blood glucose and arterial blood gas glucose point of care values.

◆ In-service training will be documented in the Study Training Log

◆ Bold signage will be displayed on all study instructions, data collection forms, and at the patient's head of bed, stating:

◆ STOP! Do not use Accuchek or other Point of Care devices to measure glucose on this patient

◆ Use only metabolic or gas lab glucose screening methods

◆ This patient is enrolled in a study with Vitamin C, which artefactually increases POC glucose testing

◆ Do Not Initiate or Utilize Sliding Scale, Scheduled Insulin, or Continuous Insulin Infusion Without Laboratory Confirmation of Blood Glucose

◆ Those receiving insulin infusion or sliding scale insulin will have metabolic glucose screening on the schedule determined by the primary physician and paid for by the study

◆ Blood glucose monitoring for insulin administration guidance should only be by a metabolic or blood gas laboratory measured blood glucose results, whether or not the study patient is receiving insulin

◆ Study personnel will follow each study patient closely to monitor insulin use to ensure that point of care glucose screening is suspended for the research subject.

◆ If subject loses central venous access (PICC line and arterial line acceptable), Vitamin C infusions are to stop but subject not

withdrawn. Data collected through end of study.

◆ Point of care glucose testing may resume 36 hours after the last infusion of study drug.

3. If the disclosure of any of the information obtained during the study would place the individual at risk for harm (legal, reputation, emotional etc.) and the information will be recorded so that the individual could be identified, explain the protections that will be put in place to decrease the risk of disclosure:

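### The glucose-meter signs and staff training work only at the site, while the protocol's own 36-hour period of unreliable readings runs about 30 hours past an assumed 24-hour discharge

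*Protocol*

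**What the plan says.** All of the following is in the Protocol.

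- **Hazard.** Risks, Discomforts, Potential Harms and Benefits, item 1, lists "interference with point of care glucometer readings (resulting in falsely high results" among the concerns with the infusions. Venous laboratory glucose is not affected.
- **Duration.** Item 2 of that section says of meter values that they "should not be considered reliable within 36 hours of the infusion, in case this is ordered clinically". Its glucose guidance closes with the rule: "Point of care glucose testing may resume 36 hours after the last infusion of study drug".
- **Room signs.** Item 2 states: "While admitted periprocedurally, signs will be posted inside and outside of the patient rooms as a warning that point of care glucose readings" cannot be trusted in that time.
- **Other signage.** "Bold signage will be displayed on all study instructions, data collection forms", and also at the head of the bed. The text is worded to staff: "STOP! Do not use Accuchek or other Point of Care devices to measure glucose on this patient". It adds: "Do Not Initiate or Utilize Sliding Scale, Scheduled Insulin, or Continuous Insulin Infusion Without Laboratory Confirmation of Blood Glucose".
- **Staff measures.** In-services go to nursing staff in the areas involved. VCU Health System, item 2, names these as the clinic, the electrophysiology suite and the inpatient units. Study personnel are also to follow each patient closely, so that meter testing stays suspended and insulin use is watched.
- **Who is kept out.** Study Population, item 5, excludes diabetics on insulin and those with HbA1c of 8% or more. Item 2 notes that in this population "point of care testing is not usually needed".
- **Schedule and stay.** Research Description, item 4, gives four 30-minute infusions at six-hour intervals (+/- 3 h), beginning on admission. The 24 h course was chosen because routine ablation patients seldom remain in hospital beyond 24 h.

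**The concern.** The protocol defines a hazard period by time since the last infusion, but its described warnings depend on the patient being on site. A short stay is a premise of the design, so most of the period can be expected to fall after the patient has gone home.

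The stated error is upward only. In an eligible diabetic not on insulin, a normal or high reading on a home meter could hide a low glucose. A falsely high reading taken elsewhere could lead a provider who knows nothing of the study to start insulin or increase glucose-lowering treatment. The bedside sign guards against the insulin step, but only where someone can see it.

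The glucose guidance is shared by all studies under the IND, and it speaks of critical care leadership, several sites and central venous access. My inference is that it was written for long inpatient stays, where bedside signs could last the full 36 h.

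**Working it through.** The 36 h figure is an input stated by the protocol. It cannot be derived from other figures there, so the check is a timeline.

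**Inputs**
- Nominal infusion starts at 0, 6, 12 and 18 h, each lasting 0.5 h (Research Description, item 4).
- Window of +/- 3 h (same item). The text does not say whether it applies to clock times or to each interval, so both are shown.
- Period of unreliable readings: 36 h after the last infusion (Risks, item 2), counted here from the end of that infusion.
- Assumption: discharge 24 h after the first infusion, or at the end of the last infusion if that is later. The protocol gives 24 h as the usual upper limit of stay, not as a discharge rule.

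**Formulas**
- End of period = end of last infusion + 36
- Hours after discharge = end of period - discharge time
- Nominal: 18 + 0.5 = 18.5; 18.5 + 36 = 54.5; 54.5 - 24 = 30.5; 30.5 / 36 = 85%

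| Dosing | Last infusion ends (h) | Period ends (h) | Discharge (h) | Hours after discharge | Share of 36 h |
|---|---|---|---|---|---|
| Nominal | 18.5 | 54.5 | 24 | 30.5 | 85% |
| Fourth infusion 3 h early | 15.5 | 51.5 | 24 | 27.5 | 76% |
| Fourth infusion 3 h late | 21.5 | 57.5 | 24 | 33.5 | 93% |
| Every interval 3 h | 9.5 | 45.5 | 24 | 21.5 | 60% |
| Every interval 9 h | 27.5 | 63.5 | 27.5 | 36.0 | 100% |

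Counting from the start of the last infusion takes 0.5 h off each result, giving 30 h nominally and 21 h at the lowest. The overall range is therefore 21 to 36 h.

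**Sensitivity to the stay.** If the 24 h run from an admission d hours before the first infusion, the nominal result is 54.5 - (24 - d) = 30.5 + d. It reaches 36 h at d = 5.5. Inpatient signs would cover the whole period only with a stay of at least 54.5 h from the first infusion (45.5 to 63.5 h on the widest reading of the window).

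**Does another contact fill the gap?**
- The daily adverse-event check in Risks, item 10, runs through study hour 24.
- Item 10 also has certain serious or unanticipated events reported through study hour 48. This covers 48 - 24 = 24 of the 30.5 h and stops 54.5 - 48 = 6.5 h short. It records events and does not prevent a misread glucose.
- The blood draw at 24 h (+/- 12 h) in Sample Collection, item 3, may fall as late as hour 36, but no glucose advice is attached to it.
- The next dated contact is the Holter at about 2 weeks (Research Description, item 4).

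**The case against.** The strongest reply is that the admission-only room sign is one measure among several. The rule on when meter testing may resume and the close follow-up by study personnel have no stated end at discharge, and read together they cover all 36 h. The diabetic exclusions go on protecting after discharge, and the in-services include clinic staff. A warning to patients would normally sit in the consent form, which was not available, or in the study instructions, which must carry the bold warning but whose audience is not stated. The chain to harm is also long. It needs an eligible diabetic with HbA1c below 8% or a patient tested elsewhere, active drug, an affected meter used within about 1.5 days, and a decision made on that reading.

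Most of this stands. A reader might infer that the plan has no protection at all after discharge, that participants go home unwarned, or that the sections contradict each other. The text supports none of these: two measures and the exclusions are not limited to the admission, the consent form cannot be judged, and no statement conflicts with another.

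What the reply does not supply is a means of carrying the 36 h rule to someone who has left the hospital. Item 2 gives study personnel no method of contact after discharge and describes no instruction to the participant or to an outside provider. A general consent warning could not give each participant's clock time, because that depends on when the last infusion ended.

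**Conclusion.** The point holds as a minor safety improvement, something the sponsor could do. On the nominal schedule with discharge assumed at 24 h, 30.5 of the 36 h (85%) lie beyond the reach of the signs and in-services. Across the dosing windows the range is 21 to 36 h, so for stays of about 24 h the gap does not close.

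These figures are hours, not risk. The protocol does not say how many eligible participants have diabetes or test at home. Among 20 patients the number exposed is small and may be zero. The conclusion rests on the assumed discharge time and on item 2 as written. A consent form with a suitable warning would narrow it to the missing clock time and the missing notice to outside providers. Neither the endpoint analysis nor the sample size is affected.

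**What to change.** Add to Risks, item 2, a discharge card given to every participant in both arms and addressed to the participant and any outside provider. It should state:

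- the clock time, calculated as the end of the last infusion + 36 h, until which normal or high point-of-care readings should not be relied on;
- that until then insulin or other glucose-lowering treatment should not be started or increased without a laboratory glucose;
- that a normal or high reading does not rule out a low glucose, and that low readings or symptoms of low glucose must still be acted on.

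If the consent form already carries a warning, item 2 should refer to it and let the card add the clock time.

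The cost is a printed card and one or two sentences of protocol text. The downside is that the card must go to both arms to keep the blind, so placebo patients also cannot rely on normal or high meter readings for about 1.5 days.

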Patients will be screened for eligibility, consented, and enrolled during their electrophysiology clinic appointment (standard of care) preceding their scheduled ablation. Based on prior experience with high dose IV ascorbic acid and the study focus on inflammatory effects, a limited list of exclusion criteria will include: diabetes mellitus with poor control or requiring insulin therapy (due to concerns that the infusions may interfere with glucometer readings), active renal calculus, active acute or chronic infection (including HIV and hepatitis C), active or recent (within 5 years) malignancy, autoimmune or auto-inflammatory disease, and recent or active use of immunosuppressive medications.

Upon admission for their ablation (standard of care), subjects will begin the first study infusion (sterile L-ascorbic acid diluted in 50mL of 5% dextrose in water or matched placebo of 50mL 5% dextrose in water). Once the subject has demonstrated no adverse effects of the first infusion, the AF ablation will proceed as scheduled. Patients will continue receiving infusions every six hours (+/- 3 hours) for a total of four infusions (research intervention). Of note, this 24 hours' worth of infusions was chosen as opposed to the 4 days' worth of infusions which was approved under the original IND (attached), since patients who are undergoing routine AF ablations rarely stay in the hospital longer than 24 hours. The shorter duration of infusions is still expected to test the theoretical benefit, while exposing the patients to even less risk of adverse reactions to the study agent than the 4 days' worth of infusions that are granted under the IND.

Prior to the first infusion, blood samples will be taken to measure plasma levels of ascorbic acid, biomarkers of inflammation (high-sensitivity C-reactive protein [hsCRP], interleukin-6 [IL-6]), and markers of blood vessel damage (von Willebrand Factor [vWF]), all part of the research intervention. A basic metabolic profile will be measured prior to the first infusion (standard of care), followed by measures of kidney function at 24 hours (+/- 12 hours) and at 30-day (+/- 14 days) follow up visit (research labs).

Patients will be monitored during their admission and during their follow up visit for any changes in blood pressure or heart rate, or any other reaction felt to be potentially related to the ablation procedure; monitoring for these elements in the history/physical

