- 3) Ability to provide informed consent and willingness to be included in the study

5. * List the study exclusion criteria:

- 1) Known allergy to Vitamin C
- 2) Inability to obtain informed consent
- 3) Diabetes mellitus either requiring the use of insulin therapy or not requiring the use of insulin therapy but which is uncontrolled, defined as a glycosylated hemoglobin of greater than or equal to 8%
- 4) Prior catheter-based ablation for atrial fibrillation
- 5) Pregnancy or breast feeding
- 6) Active renal calculus
- 7) Active acute or chronic infection (including HIV or hepatitis C)
- 8) Active or recent (within 5 years) malignancy
- 9) Autoimmune or autoinflammatory disease
- 10) Recent or active use of immunosuppressive medications

- 11) Non-English speaking
- 12) Ward of the state (inmate, other)

6. * Check all participant groups that will be included in this study or discernable in the research data/specimens. In particular, if you will know that a regulated vulnerable population (children, pregnant women, or prisoners) is involved in the study, be sure to check them:

- Healthy volunteers
- Children
- Emancipated minors
- Pregnant women
- Fetuses, Neonates, Post-delivery Materials, or In-Vitro Fertilization
- Prisoners
- Decisionally Impaired Adults
- When cancer is integral to the research - cancer patients, their family members, cancer healthcare providers, or cancer prevention
- VCU Health System or VCU Dental Care patients
- Non-VCU patients
- VCU / VCUHS students or trainees
- VCU / VCU Health System employees
- Individuals with limited English proficiency
- Active military personnel
- When researching in a K-12 environment - populations within school districts or other learning environments

7. Justify the inclusion and exclusion criteria if necessary. If you are either targeting, or excluding, a particular segment of the population / community, provide a description of the group/organization/community and provide a rationale:

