Self Referred (Flyer/Ad)

Other

4. If Other, please describe:

5. * Provide a description of:

1. How potential participants or secondary data/specimens of interest will be identified and
2. All procedures that will be followed to carry out recruitment and screening activities.

Include details (as applicable) about:

- How secondary data/specimens that meet the study's eligibility criteria will be identified (i.e. what database(s) will be queried and the search terms that will be used)
- How potential participants will be identified and their contact information obtained
- The timing and frequency of recruitment activities
- Where and how recruitment procedures will be completed
- Who will recruit or respond to potential participants
- What and how written or verbal recruitment materials and reminders (if any) will be used
- What screening activities will occur and how these procedures will be performed

See the help text for additional guidance.

Patients seen in VCUHS Electrophysiology clinics will be screened for inclusion and exclusion criteria. The investigators will request a waiver of consent to perform this screening. Patients meeting all inclusion criteria will be approached during their VCUHS clinic visit by one of the study investigators to obtain informed consent. Patients agreeing to participate in the study will sign the informed consent form and will be given a copy of the consent form. Patients who decline the consent of enrollment will not be adversely affected. Enrolled subjects will be free to withdraw from the study at any time with no adverse consequences.

6. Describe any special recruitment procedures for vulnerable populations:

7. Upload all recruitment materials including ads, flyers, telephone or in-person scripts, letters, email invitations, TelegRAM announcements, and postcard reminders:

8. * Before potential participants consent to the study, will screening questions be asked or will any screening procedures/tests be done that would not otherwise be done as standard of care:
No

9. If Yes, will identifiable information about individuals be recorded during screening:

Yes

No

Privacy

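### The risk section says patients prone to recurrent renal calculi will be excluded, but the numbered exclusion list bars only an active calculus, so the same patient is eligible under one and excluded under the other.

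*Protocol*

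**What the plan says.** Item 1 of the section Risks, Discomforts, Potential Harms and Benefits describes the renal risk of large vitamin C doses: "hyperoxaluria can be observed in 1-10% of patients, raising concerns primarily for patients with active renal calculus or those prone to recurrent renal calculi". It names two groups of concern. Item 2 of the same section, on minimizing risk, excludes both: "Patients with active renal calculus or those deemed prone to recurrent renal calculi will be excluded from the study".

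The formal answer to the request for exclusion criteria is Study Population, item 5, a list of 12. Its only stone-related entry is "6) Active renal calculus". The narrative in Research Description, item 4, also mentions only the first group, in a run that reads "active renal calculus, active acute or chronic infection (including HIV and hepatitis C), active or recent (within 5 years) malignancy".

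On how patients are selected, Potential Subject Identification and Recruitment, item 5, says: "Patients seen in VCUHS Electrophysiology clinics will be screened for inclusion and exclusion criteria". The Consent Groups table adds that those who meet every inclusion criterion and no exclusion criterion will be approached for consent.

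**The concern.** A patient with recurrent stones but no active calculus is excluded by the risk section and not excluded by the list. Hyperoxaluria is the only drug risk to which the risk section attaches a numerical frequency, and this exclusion is the only measure that item 2 offers against it. If screening follows the list, half of that measure is not carried out.

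Safety is a primary endpoint in a trial of 20 patients, so one patient of uncertain eligibility is 1/20 = 5% of the sample. A stone event in such a patient would be a protocol deviation under the risk section and an event in an eligible patient under the list, and the monitoring board could not tell which. The ambiguity also reaches the stopping criteria in item 9 of the risk section, one limb of which is that patients develop exclusion criteria after enrolment. That limb can be applied consistently only if there is one set of criteria.

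**Working it through.** The protocol gives no figure on this point, so the main check is a comparison of its sections.

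| Place | Active calculus | Prone to recurrent calculi |
|---|---|---|
| Risks, item 1 (groups of concern) | named | named |
| Risks, item 2 (risk minimization) | excluded | excluded |
| Study Population, item 5 (numbered list) | excluded (entry 6) | not listed |
| Research Description, item 4 (summary) | excluded | not listed |

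**Could another entry cover the missing group?** The other 11 concern vitamin C allergy, consent, diabetes, prior ablation, pregnancy or breast feeding, infection, malignancy, autoimmune or autoinflammatory disease, immunosuppressive medication, language, and wards of the state. None would pick up a stone history.

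**Is the risk section merely written more loosely than the list?** The other exclusion in item 2 is diabetes: insulin use, or glycosylated hemoglobin of 8% or more. Entry 3 of the list carries it over with the same threshold. So diabetes and active calculus both reached the list, and recurrent stones alone did not.

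**Is the term usable?** The protocol does not define proneness to recurrent calculi and does not say who makes that judgement.

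**Illustrative size.** The protocol gives no prevalence of recurrent stones. Assume p = 0.05 to 0.10 among candidates, independent patients, n = 20 (planned sample size) and screening by the list alone.

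- Expected number enrolled, n × p: 20 × 0.05 = 1; 20 × 0.10 = 2.
- Chance of at least one, 1 − (1 − p)^n: 1 − 0.95^20 = 0.64; 1 − 0.90^20 = 0.88.

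Only the active arm receives ascorbic acid. The protocol states no allocation ratio; under an assumed 1:1 split, n = 10 exposed.

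- Expected number exposed: 10 × 0.05 = 0.5; 10 × 0.10 = 1.
- Chance of at least one exposed: 1 − 0.95^10 = 0.40; 1 − 0.90^10 = 0.65.

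The 1-10% in item 1 is a frequency of hyperoxaluria, not of stone events, so no rate of harm follows from it.

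**The case against.** The strongest reply is that the two sections differ in completeness and do not collide outright. The list does not say that stone-prone patients are eligible, the risk section is current text of the same protocol, and an investigator who applies the whole document would exclude them. The screening forms are not shown and might ask about stone history. This stands as a limit on what can be claimed: whether such patients would be enrolled in practice is unknown. It does not remove the defect. The numbered list is the protocol's formal statement of eligibility, screening and consent are tied to the criteria, and research nurses and co-investigators are among those who obtain consent. An undefined criterion that appears only in the risk narrative is not one they can be expected to apply uniformly.

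Three smaller points are fair:

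- The Research Description summary is weak support. It is introduced as a limited list and also leaves out vitamin C allergy, prior ablation and pregnancy. The contradiction rests on the risk section and the numbered list.
- The other limb of item 9, an event known to be associated with the infusions, applies to any participant whatever the stone history. Reconciling the list would not change that limb.
- The prevalence range is not grounded in the protocol, and for drug safety the exposed-patient figures are the more relevant ones.

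The investigators' power to withdraw a patient when medically necessary (item 8) acts after enrolment and does not settle eligibility.

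**Conclusion.** The concern holds. Two current sections of the protocol give different eligibility for the same patient: one of the two groups that the safety plan says it excludes is absent from the list used to define eligibility, and the term describing that group is undefined. This follows from the text and needs no assumption. How many patients are affected does rest on assumptions. With 5% to 10% of candidates stone-prone and screening by the list alone, 1 to 2 of 20 enrolled patients would be affected, or 0.5 to 1 of about 10 exposed patients if allocation is 1:1. The gap does not touch the analysis of the inflammatory markers. Its importance lies in patient safety and in an unambiguous study population, and it should be corrected.

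**What to change.** Reconcile Study Population, item 5, with Risks, Discomforts, Potential Harms and Benefits, item 2, and bring the summary in Research Description, item 4, into line, so that every section names the same stone-related exclusion. Which rule is right is a clinical decision for the investigators. If the wider exclusion is kept, add it to the numbered list with one definition that a screener can apply from the medical history. If the narrower one is kept, correct the risk section so that it no longer describes a safeguard that the list does not contain. Carry the result into the screening form.

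The cost is about one line of text and one line on the form. Keeping the wider wording would make slightly fewer patients eligible.
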